Individuals will be analyzed by randomized group regardless of treatments received (i.e., an intention to treat analysis will be used). Analyses will utilize generalized estimating equations (GEE) to account for repeated measures on a given individual (i.e. 4, 8, 26, and 52 week measurements) for both co-primary outcomes. However, since the 26-week time point is the primary time point the treatment can only be deemed successful if the 26-week time point is successful. The other time points are considered secondary evaluations. The mean model will include an interaction between time of measurement and treatment groups (ANCOVA model) and adjustment for potential confounders and baseline outcome measurements. Omnibus tests of differences between treatment groups at each time measurement will be assessed within this GEE model framework. If the overall treatment effect is significant at a given time point then pairwise comparisons between treatment groups will be performed.

CLINICAL SIGNIFICANCE

Mean treatment effect differences exceeding 2.5 points on the Roland scale and 1.5 points on the bothersomeness scale will be considered clinically significant.

STATISTICAL POWER

When analyzing the co-primary outcomes as continuous measures, we will have 90% power to detect a 2.95 point difference in the modified Roland Score and a 1.78 point difference in Bothersomeness score. Thus, we will have ample power for detecting clinically meaningful differences since differences of 2.5 on the Roland scale and 1.5 on the bothersomeness scale are considered clinically meaningful. Assuming 11% loss to follow-up (slightly higher than was found in our previous back pain trials), we plan to recruit a total sample size of 297 participants (99 per group).

Both co-primary outcomes will be tested at the $p < 0.05$ level at each time point because they address separate scientific questions. Analyses of both co-primary outcomes at all follow-up times will be reported, imposing a more stringent requirement than simply reporting a sole significant outcome.

42

43

44

45 **1. INTRODUCTION**

46 Identifying cost-effective treatments for chronic low back pain (CLBP) remains a huge
47 challenge for clinicians, researchers, payers, and patients. About \$26 billion is spent
48 annually in the U.S. in direct costs of medical care for back pain, and in 2002, the
49 estimated costs of lost worker productivity due to back pain were \$19.8 billion. Despite

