To protect against multiple comparisons, we will use Fisher’s protected least significance approach, first testing if there is any significant difference among all 3 groups (using the omnibus Chi-Square Likelihood Ratio test). If we find a difference, we will then test for pairwise differences between groups. We will need 264 participants (88 in each group) to achieve 90% power to find either mind-body treatment different from Usual Care. This assumes that 30% of the Usual Care group and 55% of each mind body treatment group will have clinically meaningful improvement at 26 weeks, rates of improvement that are similar to those we observed in a similar back pain population in two studies (one not yet published) evaluating CAM treatments for back pain. Finally, we will have at least 80% power to detect a significant difference between MBSR and CBT if MBSR is at least 21% more effective than CBT (i.e., 76% of the

684 MBSR group versus 55% of the CBT group).

685 Our other co-primary outcome is improvement from baseline on the
686 Bothersomeness Score. With a total sample size of 264 participants, we will have 80%
687 power to find a mind-body treatment group different from Usual Care assuming that
688 47.5% of Usual Care and 69.3% of the mind body treatment groups have 30% or more
689 improvement in the bothersomeness score from baseline.

690 When analyzing the primary outcomes as continuous measures, we will have 90%
691 power to detect a 2.95 point difference in the modified Roland Score and a 1.78 point
692 difference in Bothersomeness score (assumes normal approximation to compare two
693 independent means with equal variances, a two-sided, 0.05 test with standard
694 deviations of 6.0 and 2.4 for Roland and Bothersomeness, respectively (unpublished
695 data from current study of massage for chronic back pain). Thus, we will have ample
696 power for detecting clinically meaningful differences since differences of 2.5 on the
697 Roland scale and 1.5 on the bothersomeness scale are considered clinically
698 meaningful. Assuming 11% loss to follow-up (slightly higher than was found in our
699 previous back pain trials), we plan to recruit a total sample size of 297 participants (99
700 per group).

701 Both co-primary outcomes will be tested at the $p < 0.05$ level at each time point
702 because they address separate scientific questions. Analyses of both outcomes at all

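### The 1.78-point detectable difference for bothersomeness does not fit the stated SD of 2.4, and the conclusion that power is ample for 2.5 and 1.5 points does not follow from the printed figures

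*Protocol*

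**What the plan says.** Section 9.1 sizes the trial on the proportion of participants with at least 30% improvement on the Roland scale at 26 weeks. This needs 264 evaluable participants, 88 per group, raised to 297 for 11% loss to follow-up. It then turns to the continuous scores and claims 90% "power to detect a 2.95 point difference in the modified Roland Score and a 1.78 point" difference in bothersomeness. The Highlights repeat both figures under Statistical Power.

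Section 9.1 also gives the basis. It is a normal approximation for two "independent means with equal variances, a two-sided, 0.05 test with standard" "deviations of 6.0 and 2.4 for Roland and Bothersomeness, respectively". The SDs are attributed to unpublished data from another study of chronic back pain.

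In both places the next sentence concludes that there is ample "power for detecting clinically meaningful differences since differences of 2.5 on the" Roland scale and 1.5 on the bothersomeness scale count as clinically meaningful. The Highlights adopt the same 2.5 and 1.5 points as the trial's thresholds for clinical significance.

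**The concern.** Two things look wrong.

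First, the two detectable differences share the same sample size, test and power, so they should stand in the same ratio as the SDs. The SDs are in the ratio 6.0 to 2.4, or 2.5. The printed differences are in the ratio 2.95 to 1.78, or about 1.66. The bothersomeness figure and its SD therefore cannot both be right.

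Second, the conclusion runs the wrong way. If 90% power is first reached at 2.95 and 1.78 points, power at the smaller differences of 2.5 and 1.5 is below 90%. The printed figures count against the conclusion.

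At stake is how a mean difference that misses significance is read. The power statement in the Highlights covers only the continuous scores. A reader who relies on it cannot tell how well the trial was placed to detect effects at its own thresholds for clinical significance.

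**Working it through.** **Inputs (Section 9.1).** n = 88 analysed per group (99 × 0.89 = 88.1), two-sided alpha 0.05, power 90%, normal approximation, SD 6.0 for Roland and 2.4 for bothersomeness. The sentence on continuous scores does not repeat n. Taking 88 is confirmed in step 1, where it returns the Roland figure.

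**Formula.** Detectable difference = (z₀.₉₇₅ + z₀.₉₀) × SD × √(2/n). Here 1.960 + 1.2816 = 3.2415 and √(2/88) = 0.1508, so the multiplier of the SD is 0.4887.

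**1. Roland, to reproduce the plan's own figure.** 0.4887 × 6.0 = 2.93 (2.95 with the t distribution). Power at 2.95 points is 90.3% (normal) or 90.0% (t). The printed 2.95 is right, which confirms the method and the n.

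**2. Bothersomeness.** 0.4887 × 2.4 = 1.17 (1.18 with t). Scaling the printed Roland figure gives the same: 2.95 × 2.4/6.0 = 1.18. The printed figure is 1.78.

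**3. What 1.78 would require.** The SD would have to be 1.78/0.4887 = 3.64 (or 6.0 × 1.78/2.95 = 3.62 by scaling). With SD 2.4, power at 1.78 points would be 99.8%, and 39 per group would give 90%.

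**4. Other settings.** None of these gives 1.78 at SD 2.4: n of 88 or 99, one- or two-sided tests, power of 80, 90 or 95%, two-sided alpha of 0.025, 0.0167 or 0.01, or the three-group omnibus test on 2 degrees of freedom. The results run from 0.85 to 1.40.

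**5. Power at the clinically meaningful differences.** For the unadjusted two-mean comparison with 88 per group, power = Φ(difference / (SD × √(2/n)) − 1.960).

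| Outcome | Difference | SD | Calculation | Power |
|---|---|---|---|---|
| Roland | 2.5 | 6.0 | Φ(2.764 − 1.960) | 78.9% (t: 78.5%) |
| Bothersomeness | 1.5 | 2.4 | Φ(4.146 − 1.960) | 98.6% (t: 98.5%) |
| Bothersomeness | 1.5 | 3.64 (implied by 1.78) | Φ(2.733 − 1.960) | about 78% |

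If all 99 per group were analysed, Roland power at 2.5 points would be about 83%. Reaching 90% there would take 2 × (3.2415 × 6.0/2.5)² = 121.04, so 122 analysed per group.

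**The case against.** The strongest reply is that little depends on these figures. The sample size was set on the binary Roland endpoint (30% against 55% improved), and Section 6.1 makes mean differences a secondary analysis. That stands. It limits the point to a correction of stated planning figures.

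A second reply is that the actual analysis is not an unadjusted comparison. Section 9.2 adjusts for the baseline score, partly to gain precision and power. This also stands. The protocol gives no baseline-to-follow-up correlation r, so the gain can only be shown by assumption. If 6.0 is an unadjusted SD and adjustment multiplies it by √(1 − r²), power at 2.5 Roland points is 80.5% at r = 0.2, 82.6% at 0.3, 85.4% at 0.4 and 89.1% at 0.5, passing 90% near r = 0.52. Correlation within class cohorts and the requirement of a significant omnibus test first would pull the other way. A reader might infer that the trial will miss a true 2.5-point effect more than one time in five. The documents do not support that as a statement about the planned model. The figure of about 79% belongs only to the calculation that Section 9.1 describes.

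Third, ample is a loose word, the protocol never claims 90% power at 2.5 points, and it accepts 80% power elsewhere in Section 9.1. That is fair, but the conclusion is still presented as following from the 90% figures, and it does not.

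**Conclusion.** The printed 1.78 and the SD of 2.4 are inconsistent. With 88 per group and a two-sided 0.05 test, SD 2.4 gives 1.17 (normal) to 1.18 (t), and 1.78 needs an SD of about 3.6. The conclusion that power is ample does not follow, because 2.5 and 1.5 both lie below the printed detectable differences.

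A reader might infer that 1.78 is simply a misprint for 1.18. That is plausible but not shown. The SD comes from unpublished data and is stated once, while 1.78 appears twice. If 2.4 is right, the error is conservative and power at 1.5 bothersomeness points is 98 to 99%. If 1.78 is right, that power is about 78%, and power is below 80% at both thresholds in the unadjusted calculation.

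It would also be too strong to say that precision on bothersomeness is understated by half. If SD 2.4 stands, the true detectable difference is about 34% smaller than printed (1 − 1.18/1.78). Nothing here threatens the primary analysis or the enrolment target.

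**What to change.** Check the bothersomeness SD against the unpublished data it came from. If 2.4 stands, replace 1.78 with about 1.18 in Section 9.1 and in the Highlights. If 1.78 stands, correct the SD in Section 9.1.

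In both places, replace the sentence that concludes power is ample with a statement of this kind: with 88 analysed per group, an unadjusted two-sided 0.05 comparison of two means has about 79% power for a 2.5-point Roland difference and about 98 to 99% for a 1.5-point bothersomeness difference (about 78% if the SD proves to be about 3.6); adjustment for baseline may raise these figures.

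The cost is one check at source and a change of wording in two places. The Roland statement becomes less favourable. Enrolment, tests and decision rules do not change.

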| Serious Adverse Events that are expected (see definition) in some subjects, but are determined or suspected to be occurring at a significantly higher frequency or severity than expected. | | ✓ | | ✓ |
| Expected (see definition) adverse events, serious or not serious, at least possibly related, not occurring at a higher frequency or severity than expected | | | | ✓ |
| Any event leading to the PI's concern regarding health, safety, or rights of research participants | | ✓ | | ✓ |
| Other Unexpected Adverse Events, regardless of severity, that may alter the HSRC's analysis of the risk versus potential benefit of the research because they suggest that the research places subjects or others at greater risk of physical or psychological harm than was previously known or recognized and, as a result, may warrant consideration of substantive changes in the research protocol or informed consent process / document. | | ✓ | | ✓ |
| Summarize ALL Adverse Events (whether previously reported to HSRC or not) at time of yearly continuation review) | | | | ✓ |

| | | | | |
|--|--|---|--|--|
| 
If DSM Body determines that an Adverse Event that was not previously reported to the HSRC, is now determined to also represent an Unanticipated Problem (for example due to increased frequency), then the Investigator must report it promptly to the HSRC. Include the monitoring entity's report with any actions taken with the submission to the HSRC. In addition, summarize the event(s) at time of Continuing Review.
 | |  | | |
|--|--|---|--|--|

1115
1116
1117
